4 STUDY DESIGN

This is a randomized, double-blind, placebo-controlled, cross-over study to determine if DHEA-S will increase FEV₁ and decrease FeNO.

4.1 MULTIPLE DOSE STUDY

The dose of DHEA will be 100 mg via slow release (SR) capsules. Subjects will take one capsule daily at the same time each day.

4.2 PROJECTED STUDY ENROLLMENT

The study cohort will consist of 30 subjects with asthma.

5 STUDY SUBJECT ELIGIBILITY

5.1 INCLUSION CRITERIA

1. Adult male or female age ≥ 18 and ≤ 50 years at the time of enrollment
2. Evidence of asthma demonstrated by reversibility at visit 0 or by historical methacholine or bronchodilator reversibility if testing was performed under either the 2017 ERS technical standard (22) or the 1999 ATS Guidelines (23) or outside studies, provided that full sets of flow volume loops have been reviewed and approved by the PI. These criteria are defined as one of the following:
 - a. For bronchodilator reversibility: An increase in $FEV_1 \geq 10\%$ (24) compared to the baseline (and 200 ml) after up to 8 puffs of albuterol
 - b. For historical methacholine responsiveness: Positive methacholine defined as $PC20 \leq 16$ mg/ml, or $PD20 \leq 400$ mcg
3. Physician diagnosis of asthma according to NHLBI guidelines
4. Consistent use of an ICS inhaler for the prior 2 months
5. Non-smoker
6. Females must not be pregnant or breastfeeding
7. Absence of non-allergic comorbidities

5.2 EXCLUSION CRITERIA

1. Pregnant or actively trying to become pregnant; breastfeeding
2. Positive urine pregnancy test
3. Known lung disease other than asthma
4. Acute (non-asthma related) dyspnea, viral respiratory illness or asthma exacerbation within 4 weeks of screening
5. Systemic glucocorticoid dosing for maintenance >10 mg/day of prednisone or equivalent
6. Patients with significant non-allergic comorbidities (e.g. cerebral palsy, heart disease, kidney disease, liver disease, etc.)
7. Patients with any known central or peripheral endocrine abnormality such as precocious puberty or diabetes
8. Patients with any known previous adverse reaction to DHEA
9. Current smoker or pack year history > 5 years (includes vaping/nicotine inhalation devices)
10. Positive urine cotinine test (> 100 mg/mL)
11. Use of prednisone or antibiotics in the last 4 weeks
12. Use of any performance-enhancing drugs in the last 2 weeks
13. Use of DHEA in the last 2 weeks
14. Androgen use for any reason.

15. Any other condition or finding that would compromise the safety of the subject or the quality of the study data, or otherwise interfere with achieving the study objectives, as determined by the PI
16. Menopausal amenorrhea by history
17. Positive PSA (>4 ng/ml) (Prostate Specific Antigen)
18. Prior diagnosis of vocal cord dysfunction, bronchopulmonary dysplasia, cystic fibrosis, chronic obstructive pulmonary disorder, or other lung disease
19. Systolic blood pressure > 150 mm Hg and/or diastolic blood pressure >90 mm Hg
20. Heart rates outside the range of 50 to 120 beats per minutes or with a pathologic irregularity
21. Patients afflicted with any additional acute or chronic pathology that in the opinion of the screening physician makes them unsuitable for study or increases the risks associated with the study.

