7 DESCRIPTION OF EVENTS

Medical history and demographics, height, weight and vital signs

Relevant medical history, including history of current disease, spirometry results, other pertinent respiratory history, and information regarding underlying diseases will be recorded. Demographic and baseline clinical characteristics including age, gender, and race will be recorded. Pulse oximetry, height (at screening only) and weight will be measured, as well as vital signs (blood pressure, temperature, heart rate and respiration rate).

Concomitant medications

All concomitant medications and concurrent therapies will be documented at visit 0. Dose, route, unit frequency of administration, and indication for administration and dates of medication will be captured for the 30 days prior to screening and during the study. The document will be reviewed and addended (if needed) at each visit.

Asthma questionnaires

Subjects will be asked to complete two questionnaires: the Asthma Control Test (ACT) and the Asthma Control Questionnaire (ACQ).

- The ACT is a validated asthma assessment tool used to assess asthma symptoms over a 4-week period. Each item on the ACT has a possible score ranging from 0 to 5, and the total score is used to determine asthma control.
- The ACQ includes six questions on symptoms, activity limitation and beta2-agonist use, with an optional assessment on airway caliber over a 7-day period. Each question is scored from 0 (well controlled) to 6 (extremely poorly controlled) with the total score being the average of the questions.

Urine pregnancy test

A urine pregnancy test will be performed at Visits 0 and Visit 1 (if not the same day as screening visit) if the subject is a female of child bearing potential.

Urine cotinine test

A urine cotinine test will be performed at Visit 0 for all subjects to measure cotinine levels.

Prostate specific antigen test

Blood will be obtained from male subjects for PSA because administration of supplemental DHEA in people with prostate cancer could theoretically result in a flare-up of their prostate cancer.

Spirometry with maximum bronchodilator response

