8 DESCRIPTION OF VISITS

Below are the visits and the interventions that may occur at each of the visits. In addition to the following scheduled visits, we are also including an unscheduled visit that may be used for any reason when a subject needs to return to the study site to complete study activities.

Visit 0 (Screening Visit)

1. Review the study with the subject and obtain written informed consent and HIPAA authorization
2. Assign the subject a unique subject id number
3. Complete asthma control test and asthma control questionnaire
4. Record demographics and other baseline data

5. Record medical and surgical history, including a history of asthma, diagnosis date, and asthma signs and symptoms
6. Record concomitant medications
7. Review inclusion/exclusion criteria
8. Measure and record height and weight without shoes
9. Perform and record vital signs, including blood pressure after the subject has been seated for 5 minutes
10. Perform and record oximetry
11. Perform abbreviated physical exam
12. Obtain urine to perform urine pregnancy test (when applicable) and urine cotinine test
13. Obtain blood for prostate specific antigen test (when applicable)
14. Perform spirometry with maximum bronchodilator response
15. Perform FeNO
16. Obtain blood
17. Record any adverse events (AEs) that may have occurred since signing consent
18. Schedule MCT or Visit 1

MCT Visit, if needed (Anytime between days 1-7, must be at least 3 days prior to Visit 1)

1. Confirm ongoing consent to participate
2. Collect urine for pregnancy test if applicable
3. Record vital signs and weight
4. Complete MCT checklist
5. Perform and record MCT
6. Confirm eligibility criteria
7. Record adverse events
8. Schedule Visit 1

Visit 1 (Day 7 ± 3)

1. Complete asthma control test and asthma control questionnaire
2. Review and record any changes to concomitant medications
3. Record any adverse events (AEs) that may have occurred since last visit
4. Measure and record weight without shoes
5. Perform and record vital signs, including blood pressure after the subject has been seated for 5 minutes
6. Perform and record oximetry
7. Perform abbreviated physical exam
8. Obtain urine to perform urine pregnancy test (when applicable)
9. Perform spirometry
10. Perform FeNO
11. Obtain blood
12. Give subject a dosing and symptom diary and instructions on dosing intervals
13. Randomize to receive placebo or DHEA-S
14. Send home with 28 days of DHEA-S or placebo capsules
15. Schedule visit 2

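### The cotinine exclusion threshold is written as 100 mg/mL, a concentration urine cannot reach, so as written the criterion can exclude nobody

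*Protocol*

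**What the plan says.** Protocol section 5.2, exclusion criterion 10, excludes a subject with a "Positive urine cotinine test (> 100 mg/mL". This is the only place where a cotinine cut-off appears.

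The test is named in three other places, each time without a unit or a threshold:

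- Section 6 (Scheduled Events) places it at Visit 0 only.
- Section 7 (Description of Events) says "A urine cotinine test will be performed at Visit 0 for all subjects to measure cotinine levels".
- Section 8 (Description of Visits) lists under Visit 0 "Obtain urine to perform urine pregnancy test (when applicable) and urine cotinine test".

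Two further criteria cover smoking without a laboratory test. Section 5.1, inclusion criterion 5, requires a non-smoker. Section 5.2, exclusion criterion 9, removes a "Current smoker or pack year history > 5 years (includes vaping/nicotine inhalation devices".

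The other blood or urine concentration limit in the exclusion list is criterion 17, "Positive PSA (>4 ng/ml) (Prostate Specific Antigen". It has the same form: the word positive, followed by a number in brackets.

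**The concern.** The bracket in criterion 10 defines what counts as positive, and it does so at a concentration that looks physically impossible in urine. If the number is the decision rule, the criterion has no effect.

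At stake is the detection of undisclosed nicotine use. The protocol names no other objective check behind inclusion 5 and exclusion 9, and this one is done once, at screening. FEV₁ and FeNO are secondary objectives (section 3.2), and section 4 describes the study as designed to show effects on both. If smoking affects either measure, which is assumed here because the protocol does not discuss it, undetected users add noise and change the population studied. The planned cohort is 30 (section 4.2), so three such subjects would be 3/30 = 10% of it.

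**Working it through.** **Inputs from the protocol.** The threshold is more than 100 mg/mL (section 5.2, item 10). The PSA limit is more than 4 ng/ml (section 5.2, item 17). The protocol gives no derivation of the cotinine figure, so there is nothing to reproduce.

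**Inputs assumed, not in the protocol.** Nicotine intake is 10 to 200 mg a day. Urine volume is 0.5 to 2 L a day. Molecular weights are 162.2 for nicotine and 176.2 for cotinine. All nicotine is taken to leave the body as urinary cotinine, which gives an upper bound.

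**Step 1: convert the unit.**

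- 100 mg/mL × 1,000 mL/L ÷ 1,000 mg/g = 100 g/L
- 100 g/L = 10 g per 100 mL = 10% weight/volume
- 100 mg/mL × 1,000,000 ng/mg = 100,000,000 ng/mL

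**Step 2: daily excretion needed to reach the threshold.** Excretion = 100 g/L × urine volume.

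- At 0.5 L a day: 50 g of cotinine a day
- At 2 L a day: 200 g of cotinine a day

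**Step 3: highest concentration that intake could produce.** Concentration (mg/mL) = intake (mg/day) × (176.2 / 162.2) ÷ urine volume (mL/day).

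| Nicotine, mg/day | Urine, L/day | Upper bound, mg/mL | Threshold ÷ upper bound |
|---|---|---|---|
| 10 | 1.5 | 0.0072 | 13,808 |
| 10 | 0.5 | 0.0217 | 4,603 |
| 30 | 1.5 | 0.0217 | 4,603 |
| 30 | 0.5 | 0.0652 | 1,534 |
| 100 | 0.5 | 0.2173 | 460 |
| 200 | 0.5 | 0.4345 | 230 |

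For the last row: 200 × 1.0863 ÷ 500 = 0.4345 mg/mL, and 100 ÷ 0.4345 = 230. A urine volume of 2 L lowers every value further. No combination in the assumed range comes closer than a factor of about 230.

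**Step 4: is the bracketed number the rule?** Criteria 10 and 17 are built the same way. The footnote to the schedule in section 6 treats the PSA number as operative: a male subject whose result exceeds it is told he cannot take part. Section 7 says the cotinine test measures levels, which fits a numeric rule. Read in the same way, criterion 10 can never be met.

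**Step 5: size of the slip if only the prefix is wrong.** 100,000,000 ng/mL ÷ 100 ng/mL = 1,000,000. This is conditional, because the protocol does not state the intended cut-off.

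**The case against.** The best case against treating this as more than a typing error has four parts.

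- **Sites will use the assay's own positive call.** The criterion opens with the word positive, and the protocol does not say whether the assay is quantitative or a kit with a built-in cut-off. No one is likely to apply 100 mg/mL in earnest. This is probably true in practice, but the site would then be excluding people whom the written number admits.
- **Other criteria still allow exclusion.** Exclusion 9 does not limit the evidence for current smoking, so a raised cotinine result could count under it. Exclusions 15 and 21 give the investigator and the screening physician discretion over findings that threaten data quality or suitability. This stands: what is lost is an automatic, uniform trigger, not all power to exclude.
- **The cross-over limits the damage.** Each subject receives both treatments, so stable smoking largely cancels in the within-subject comparison. The affected measures are secondary, since the primary objective is ACQ/ACT. This also stands, although it does not cover habits that change between periods or a treatment effect that differs in smokers, and it does not restore the intended population.
- **The PSA unit proves nothing about cotinine.** It is a different analyte in a different fluid. This is fair as to what the correct cotinine unit should be. The PSA criterion matters only because it shows how bracketed limits in this list are used.

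The first three points reduce the practical impact. None of them makes the number right, and no other section of the protocol corrects it.

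**Conclusion.** The concern holds. As a numeric rule, exclusion criterion 10 can exclude 0% of subjects, because its threshold lies at least about 230 times above any urinary cotinine level in the assumed range, and roughly 1,500 to 14,000 times above it at 10 to 30 mg of nicotine a day and 0.5 to 1.5 L of urine. The unit conversion rests on the protocol alone. The impossibility rests on the stated intake and volume assumptions, and the margin is too wide for any reasonable change in them to matter.

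The consequence is limited to the biochemical criterion: history-based exclusion and investigator discretion remain. The effect on the trial's results cannot be sized from the protocol, which gives no expected number of undisclosed users. No sample size, power or significance level is affected. The point should be corrected, but it does not threaten the design.

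**What to change.** In section 5.2, item 10, replace the unit with the one reported by the assay in use. A ng/mL unit appears to be intended, but the protocol does not establish the cut-off, so confirm both number and unit against the kit or laboratory documentation. Put the same figure on the eligibility checklist. It would help to repeat it in the section 7 test description, which currently gives no cut-off.

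If screening has begun, check which cut-off the site has actually been applying and record it, so that the enrolled population can be described correctly.

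The cost is a one-word protocol correction. It adds no subjects, visits or procedures.

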6 SCHEDULED EVENTS

Assessments and Procedures	Visit 0	MCT	Visit 1	Visit 2	Visit 3	Visit 4	Visit 5	Visit 6
	Screening Day 0	Anytime between days 1-7; at least 3 days prior to Visit 1	Day 7 ± 3 days	Day 21 ± 3 days (phone visit)	Day 35 ± 3 days	Day 63 ± 3 days	Day 77 ± 3 days (phone visit)	Day 91 ± 3 days
Informed consent	X							
Medical history and demographics	X							
Concomitant medications	X		X	X	X	X	X	X
Review inclusion/exclusion criteria	X							
Asthma Control Test (ACT) & Asthma Control Questionnaire (ACQ)	X		X	X	X	X	X	X
Height	X							
Weight, pulse oximetry, vital signs	X	X	X		X	X		X
Urine pregnancy test (when applicable)	X	X	X		X	X		X
Urine cotinine test	X							

Assessments and Procedures	Visit 0	MCT	Visit 1	Visit 2	Visit 3	Visit 4	Visit 5	Visit 6
	Screening Day 0	Anytime between days 1-7; at least 3 days prior to Visit 1	Day 7 ± 3 days	Day 21 ± 3 days (phone visit)	Day 35 ± 3 days	Day 63 ± 3 days	Day 77 ± 3 days (phone visit)	Day 91 ± 3 days
Prostate specific antigen test ¹ (when applicable)	X							
Spirometry with bronchodilator response (maximum bronchodilator)	X							
Spirometry. If ≥ 10% decrease in FEV ₁ from baseline, give bronchodilator and measure response			X		X	X		X
Methacholine Checklist ^a		X						
Methacholine Challenge Test (MCT) (Asthma Participants Only) ^a		X						
FeNO	X		X		X	X		X
Abbreviated physical exam	X		X		X	X		X
Blood draw	X		X		X	X		X
DHEA/placebo capsules dispensed in labeled bottle			X			X		
Collect any unused DHEA/placebo capsules					X			X
Adverse events	X	X	X	X	X	X	X	X
Give Dosing & Symptom Diary			X			X		

¹ This test is for male subjects only. The prostate specific antigen is a protein made by the prostate and found in blood. If the result of this test is >4 nanograms per milliliter, subjects will be informed they are unable to participate in the study. We will also call them prior to their next visit to let them know and recommend that they follow-up with their regular primary care physician.

Assessments and Procedures	Visit 0	MCT	Visit 1	Visit 2	Visit 3	Visit 4	Visit 5	Visit 6
	Screening Day 0	Anytime between days 1-7; at least 3 days prior to Visit 1	Day 7 ± 3 days	Day 21 ± 3 days (phone visit)	Day 35 ± 3 days	Day 63 ± 3 days	Day 77 ± 3 days (phone visit)	Day 91 ± 3 days
Collect Dosing & Symptom Diary					X			X

^aThe MCT and MCT with checklist done only if: 1) participants with asthma fail to demonstrate 10% reversibility in FEV1 (max BD testing) and there is no historical MCT available

7 DESCRIPTION OF EVENTS

Medical history and demographics, height, weight and vital signs

Relevant medical history, including history of current disease, spirometry results, other pertinent respiratory history, and information regarding underlying diseases will be recorded. Demographic and baseline clinical characteristics including age, gender, and race will be recorded. Pulse oximetry, height (at screening only) and weight will be measured, as well as vital signs (blood pressure, temperature, heart rate and respiration rate).

Concomitant medications

All concomitant medications and concurrent therapies will be documented at visit 0. Dose, route, unit frequency of administration, and indication for administration and dates of medication will be captured for the 30 days prior to screening and during the study. The document will be reviewed and addended (if needed) at each visit.

Asthma questionnaires

Subjects will be asked to complete two questionnaires: the Asthma Control Test (ACT) and the Asthma Control Questionnaire (ACQ).

- The ACT is a validated asthma assessment tool used to assess asthma symptoms over a 4-week period. Each item on the ACT has a possible score ranging from 0 to 5, and the total score is used to determine asthma control.
- The ACQ includes six questions on symptoms, activity limitation and beta2-agonist use, with an optional assessment on airway caliber over a 7-day period. Each question is scored from 0 (well controlled) to 6 (extremely poorly controlled) with the total score being the average of the questions.

Urine pregnancy test

A urine pregnancy test will be performed at Visits 0 and Visit 1 (if not the same day as screening visit) if the subject is a female of child bearing potential.

Urine cotinine test

A urine cotinine test will be performed at Visit 0 for all subjects to measure cotinine levels.

Prostate specific antigen test

Blood will be obtained from male subjects for PSA because administration of supplemental DHEA in people with prostate cancer could theoretically result in a flare-up of their prostate cancer.

Spirometry with maximum bronchodilator response

Pre-bronchodilator FEV₁ and post-bronchodilator FEV₁ will be measured using spirometry. The FEV₁ is the volume of air which can be forcibly exhaled from the lungs in the first second, measured in liters. Spirometry will be done according to American Thoracic Society/European Respiratory Society procedural guidelines (25). Current reference equations (26) will be used.

Airway Reversibility

Airway reversibility will be demonstrated by measuring the change in FEV₁ before and after inhalation of albuterol; reversibility testing should be attempted after withholding long-acting beta-agonist (LABA) therapy for at least 12 hours and short-active beta agonist (SABA) therapy for at least 6 hours. Up to 8 puffs of albuterol should be used for reversibility testing, as tolerated. If a subject's FEV₁ improves at least 10% between the 2 tests, then he/she will be deemed as having airway reversibility.

Methacholine Challenge Test (MCT)

MCT will be performed only in participants with asthma who do not demonstrate reversibility and with a pre-diluent FEV1 of >50% predicted and at least 1.0 liter. A physician will be available during the challenge and testing will be performed according to standard of care. Participants will not be discharged until their FEV1 is within 10% of their baseline FEV1.

FeNO

FeNO stands for Fractional Exhaled Nitric Oxide and it is a non-invasive procedure that is considered to be an indirect measurement of airway inflammation. It involves taking a deep breath and blowing air out into a mouth piece at a constant pressure as directed by the study team. Measurements will be recorded.

Medication withhold:

To prepare for lung function testing, subjects will be asked to withhold certain medications so that screening procedures produce the most accurate results. Subjects will receive a list of medications that must be withheld prior to certain study visits, and length of withholding time.

Abbreviated physical exam

An abbreviated physical exam will consist of HEENT, cardiovascular system, chest/lung, abdomen, extremities, skin, and any other areas as appropriate. This exam will be performed by a physician.

Blood collection

Blood will be drawn at visits 0, 1, 3, 4, and 6. A CBC with differential and comprehensive metabolic panel will be performed as safety labs throughout the study. A prostate specific antigen (PSA) level will be measured in male subjects at the screening visit. DHEA-S levels will be measured at the screening visit and at the conclusion of the study. Blood will also be used for measurements including but not limited to: cytokine responses, hormone levels, PBMCs, genomics, and DHEA. The maximum amount of blood to be obtained at each visit is up to 40 ml.

Genotyping

Single nucleotide polymorphism testing for HSD3B1 genotype will be performed from blood drawn at the screening visit and results must be available before the first dose of study drug. If a genotype test has been performed previously and is documented in the subject's medical or research records, the subject's eligibility must be approved by the PI. If a historic genotype result is not available at screening or if the historic genotype result is not approved by the medical monitor, subjects will be tested for genotype at screening and the results must be reviewed before the first dose of study drug. Subjects will not receive the study drug if genotype is not confirmed by both an approved historic genotype and approval of medical monitor result OR by genotype testing at screening. Study subjects with HSD3B1 AA or AC specific variants will be enrolled in the study. No further genetic studies will be performed on the subject's DNA. The subject will be fully informed of the genotype results relevant to this study.

DHEA

DHEA is available as an over-the-counter supplement that is available on the market without prescription. The DHEA used in this study will be formulated for slow release and will be dispensed at a compounding pharmacy by prescription only. They produce 100mg capsules that will be used for this study. The prescribed DHEA capsules will be received, stored and distributed by the [name] Pediatric Translational Research Lab Group in the Herman B Wells Center for Pediatric Research. Accountability records will be maintained by the study team.

Randomization

Randomization will occur at the compounding pharmacy that manufactures DHEA and placebo. The study drug will be distributed with a code and study team will be blinded from code. Only the compounding pharmacy and the DSMB will have access to the unblinded data.

Dosing and Symptom diary

Subjects will complete a dosing and symptom diary at home starting after visit 1 until the end of the study.

Adverse events (AEs)

Information regarding the occurrence of AEs will be captured throughout the study from Visit 0 until the final visit. Subjects will be given a phone number to notify the study coordinator regarding an asthma exacerbation or other adverse event.

